7.14 Storage of Blood Samples in the Study

The leftover of samples that are left after the analysis per protocol is complete and other remaining samples (of all samples except for samples taken for clinical laboratory tests) will be stored for up to 15 years for future additional research. Patients will be asked to confirm if

argenx

ARGX-113-1602, Version 2.0

ARGX-113

they allow additional storage of samples in the study ICF to address any scientific questions related to ARGX-113 or MG.

8.0 SAFETY, EFFICACY, PHARMACOKINETIC, AND PHARMACODYNAMIC ASSESSMENTS

8.1 Safety

Safety assessments will consist of monitoring and recording all AEs, including SAEs, and pregnancies; suicidality assessment; safety laboratory testing, measurement of vital signs, ECGs, physical examinations; and other tests that are deemed critical to the safety evaluation of the study in all patients who receive at least 1 dose of the IMP. As discussed in [Section 8.1.1.4](#), any pregnancy that occurs while a patient is enrolled in the study will also be monitored and reported according to the appropriate regulations.

8.1.1 Adverse Events

The Investigator is responsible for recording all AEs observed during the study from the time the patient signs the ICF until the last contact of the patient.

Definition of AE: An AE is any untoward medical occurrence in a clinical study patient whether or not a pharmaceutical product is administered and which does not necessarily have a causal relationship with this treatment. An AE can therefore be any unfavorable and unintended sign (including an abnormal laboratory finding), symptom, or disease temporally associated with the use of a medicinal product or IMP, whether or not considered related to the medicinal product or IMP.

An AE can also be a new disease or exacerbation of an existing disease (a worsening in the character, frequency, or severity of a known condition).

Abnormal laboratory values, or test results, physical examination findings, and other abnormal investigational findings (i.e., ECG) should not be reported as AEs unless they are associated with clinical signs and symptoms that are considered clinically significant, require therapy (e.g., hematologic abnormality that requires transfusion or hematological stem cell support), or lead to treatment discontinuation.

Death is not considered an AE but an outcome.

Disease progression can be considered as a worsening of a patient's condition attributable to the disease for which the IMP is being studied. It may be an increase in the severity of the disease under study and/or increase in the symptoms of the disease and should be considered as disease progression and not an AE.

Adverse Drug Reaction (ADR): Any untoward and unintended response in a subject to an IMP which is related to any dose administered to that subject.

Definition of Serious AE (SAE): An SAE, experience or reaction, is any untoward medical occurrence (whether considered to be related to IMP or not) that at any dose:

- Results in death;
- Is life-threatening (the patient is at a risk of death at the time of the event; it does not refer to an event which hypothetically might have caused death if it were more severe);
- Requires inpatient hospitalization or prolongation of existing hospitalization: Hospital admissions and/or surgical operations planned before a study are not considered SAEs or if the illness or disease which caused hospitalization existed before the patient was enrolled in the study, provided that it did not deteriorate in an unexpected way during the study. However, the condition for which the surgery is required may be an AE.
- Results in persistent or significant disability or incapacity;
- Is a congenital abnormality or birth defect;
- Other: Medically significant events, which do not meet any of the criteria above, but may jeopardize the patient and may require medical or surgical intervention to prevent one of the other serious outcomes listed in the definition above. Examples of such events are blood dyscrasias (e.g. neutropenia or anemia requiring blood transfusion, etc.) or convulsions that do not result in inpatient hospitalization.

Suspected Unexpected Serious Adverse Reactions and Unexpected Adverse Reactions

Any suspected adverse reaction that is serious, unexpected, and considered to be related to drug exposure is defined as a suspected unexpected serious adverse reaction (SUSAR).

An unexpected AE is any adverse drug event, which is not listed in the current Investigator's Brochure or is not listed at the specificity or intensity that has been observed.

Suspected adverse reaction means any AE for which there is a reasonable possibility that the drug caused the AE. The following examples provide types of evidence that would suggest a causal relationship between the IMP and the AE:

- A single occurrence of an event that is uncommon and known to be strongly associated with drug exposure (e.g., angioedema, hepatic injury, Stevens-Johnson Syndrome)

- One or more occurrences of an event that is not commonly associated with drug exposure, but is otherwise uncommon in the population exposed to the drug (e.g., tendon rupture)
- An aggregate analysis of specific events observed in a clinical study (such as known consequences of the underlying disease or condition under investigation or other events that commonly occur in the study population independent of drug therapy) that indicates those events occur more frequently in the drug treatment group than in a concurrent or historical control group.

An untoward and unintended post-dosing response to a non-study drug is, by definition, not a SUSAR, but is, however, an AE.

Each AE is to be evaluated for duration, severity, seriousness and causal relationship to the IMP or study procedures. The action taken with the investigational drug and the outcome of the event must also be recorded.

Overdose

For the purposes of this study, exceeding the dosage requirements specified in this protocol represents an overdose. In case of suspected overdose, the patient should be treated according to standard medical practice based on the Investigator's judgment.

Severity

All AEs observed will be graded using the National Cancer Institute (NCI) Common Terminology Criteria for Adverse Events (CTCAE) version 4.03. The NCI CTCAE is a descriptive terminology which can be utilized for AE reporting. A grading (severity) scale is provided for each AE term. Grade refers to the severity of the AE. If a particular AE's severity is not specifically graded by the guidance document, the Investigator is to use the general NCI-CTCAE definitions of Grade 1 through Grade 5 following his or her best medical judgment. The CTCAE displays Grades 1 through 5 with unique clinical descriptions of severity for each AE based on the following general guideline:

- Grade 1: Mild; asymptomatic or mild symptoms; clinical or diagnostic observations only; intervention not indicated.
- Grade 2: Moderate; minimal, local or non-invasive intervention indicated; limiting age-appropriate instrumental activities of daily living (ADL).

- Grade 3: Severe or medically significant but not immediately life-threatening; hospitalization or prolongation of hospitalization indicated; disabling; limiting self-care activities of daily living (ADL).
- Grade 4: Life-threatening consequences; urgent intervention indicated.
- Grade 5: Death related to AE.

Relationship

The causal relationship between the IMP/study procedures and the AE has to be characterized as unrelated, unlikely, related, possible, and probable.

- Events can be classified as “unrelated” if there is not a reasonable possibility that the IMP caused the AE.
- An “unlikely” relationship suggests that only a remote connection exists between the IMP and the reported AE. Other conditions, including chronic illness, progression or expression of the disease state, or reaction to concomitant medication, appear to explain the reported AE.
- A “related” relationship suggests that the AE follows a reasonable temporal sequence from administration of IMP, it follows a known or expected response pattern to the IMP, and it cannot reasonably be explained by known characteristics of patient’s clinical state.
- A “possible” relationship suggests that the association of the AE with the IMP is unknown; however, the AE is not reasonably supported by other conditions.
- A “probable” relationship suggests that a reasonable temporal sequence of the AE with drug administration exists and, in the Investigator’s clinical judgment, it is likely that a causal relationship exists between the drug administration and the AE, and other conditions (concurrent illness, progression or expression of disease state, or concomitant medication reactions) do not appear to explain the AE.

In final evaluation for reporting the relationship will be converted into “Binary Determination” as per CIOMS. Unrelated and Unlikely will be clubbed into “Unrelated” and Related, Possible and Probable will be clubbed into “Related” for final reporting purpose.

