8.1.1.1 Reporting of Adverse Events and Serious Adverse Events

All AEs, that occur during the study from signature of informed consent until EoS (Visit 16), are to be recorded on the appropriate AE pages (either ‘serious’ or ‘non-serious’) in the

eCRF. The Investigator should complete all the details requested, including dates of onset, stop date (when applicable), severity, action taken, outcome, and relationship to IMP, and to study procedures. Each event should be recorded separately in the eCRF.

All AEs spontaneously reported by the patient or reported in response to the open question from the study personnel: 'Have you had any health problems since the previous visit/you were last asked?', or revealed by observation will be collected and recorded in the eCRF. When collecting AEs, the recording of diagnoses is preferred (when possible) to recording a list of signs and symptoms. However, if a diagnosis is known and there are other signs or symptoms that are not generally part of the diagnosis, the diagnosis and each sign or symptom will be recorded separately.

Any SAE, including death due to any cause, which occurs during this study after signature of informed consent, whether or not related to the IMP, must be reported immediately (within 24 hours of the study site's knowledge of the event). All SAEs will be recorded (within 24 hours) on the electronic SAE report form and the AE form in the eCRF, the Investigator or delegated site staff should check that all entered data is consistent. An alert email for the SAE report will then be automatically sent by email to the Sponsor's designated CRO (Quintiles) safety mailbox via the electronic data capture (EDC) system. In case the EDC system is not functioning correctly or the system is down, all SAEs should be reported by fax/email to Sponsor's designated CRO (Quintiles) using the SAE paper report form.

The report will contain as much available information concerning the SAE to enable the Sponsor (or an authorized representative) to file a report, which satisfies regulatory reporting requirements. These timelines apply to initial reports of SAEs and to all follow-up reports.

Criteria for documenting the relationship to IMP as well as severity, outcome, and action taken will be the same as those previously described.

All SAEs that are spontaneously reported within 30 days of a patient's last visit are to be collected and reported as previously described.

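### The hospitalisation criterion for SAEs exempts pre-existing illness without requiring a planned admission, so an unplanned admission for expected worsening of a comorbidity can be classed as non-serious

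*Protocol*

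**What the plan says.** The hospitalisation bullet in the SAE definition (Protocol 8.1.1) carries two exemptions in one sentence.

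- The first concerns elective care: "Hospital admissions and/or surgical operations planned before a study are not considered SAEs".
- The second, introduced by *or if*, concerns a prior condition: "or disease which caused hospitalization existed before the patient was enrolled in the study, provided that it did not deteriorate in an unexpected way".

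The bullet closes with a reminder about surgery only: "However, the condition for which the surgery is required may be an AE". A later bullet adds a residual criterion: "Other: Medically significant events, which do not meet any of the criteria above, but may jeopardize the patient".

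The same section counts worsening of an existing illness as a possible AE ("An AE can also be a new disease or exacerbation of an existing disease") and describes a Grade 3 event partly by "hospitalization or prolongation of hospitalization indicated". Expedited reporting in 8.1.1.1 attaches to seriousness: it covers "Any SAE, including death due to any cause, which occurs during this study after signature of informed consent, whether or not related to the IMP", with a limit of 24 hours from the site's knowledge.

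SAE incidence is part of the primary endpoint (Protocol 4.1). SAP 16.1 counts subjects with at least one serious TEAE and at least one related serious TEAE.

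**The concern.** The second exemption makes seriousness depend on whether a deterioration was expected. Seriousness normally records what happened to the patient, here an admission. Whether the worsening was foreseeable is a different question, and the protocol's SUSAR definition already treats serious and unexpected as separate conditions.

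The trial gives the drug to patients with MG for the first time (Protocol 5.2). It lowers IgG, and patients may also be on steroids and other immunosuppressants (Protocol 5.3.1, criterion 5). An infective flare of a long-standing condition is therefore a plausible form of harm. It is also an event that a site could describe as pre-existing and expected. If such an admission is recorded as non-serious on that ground, the decision is taken by the individual investigator before any expedited review, and the primary safety summary takes it over.

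**Working it through.** No figure in the plan is at issue, so the check is mainly a reading of the text.

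**1. Is the second exemption limited to planned admissions?** The first clause exempts planned admissions and operations without further condition. The second is a separate alternative with two conditions: the illness existed before enrolment, and it did not deteriorate unexpectedly. Neither mentions planning. Enrolment is the signing of consent (Protocol 6.1), so any comorbidity present at consent qualifies. Nothing elsewhere in the protocol or SAP narrows the clause.

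**2. Is unexpected deterioration defined?** The only related definition in 8.1.1 concerns an adverse drug event not listed in the Investigator's Brochure, or not at the observed specificity or intensity. That is a test of product information and does not tell a site how to judge the course of a comorbidity.

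**3. What happens to an exempted event?** Take an unplanned admission for a comorbidity flare that the investigator considers expected, with no other seriousness criterion met.

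| Step | Source | Result |
|---|---|---|
| Is it an AE? | Protocol 8.1.1: "a worsening in the character, frequency, or severity of a known condition" | Yes, it can be |
| Severity | Protocol 8.1.1, Grade 3 description | May be Grade 3 |
| Hospitalisation criterion | Protocol 8.1.1, second exemption | Not met |
| 24-hour report | Protocol 8.1.1.1, SAEs only | Not triggered |
| SUSAR assessment | Protocol 8.1.1, must be serious | Not reached |
| Serious TEAE count | SAP 16.1 | Not counted |
| Grade 3 or higher TEAE count | SAP 16.1 | May be counted |

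SAP 16.1 has worst-case rules for missing relationship and missing severity. It has no rule that re-derives seriousness, so the site's classification stands.

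**4. Scale.** The input is 12 patients per arm (Protocol 10.1). One patient reclassified changes that arm's SAE incidence by 1/12 = 8.3 percentage points. With exact (Clopper-Pearson) 95% limits:

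- 1/12 = 8.3%, limits 0.2% to 38.5%.
- 0/12 = 0%, upper limit 1 − 0.025^(1/12) = 26.5%.

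These show what one patient is worth at this sample size. They are not an estimate of how many events would be affected.

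**The case against.** The case on the other side has five parts.

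- **Other criteria remain.** The exemption sits inside the hospitalisation bullet only. Death, life-threatening events, disability and the medically significant criterion still apply, and an exempted event is open to the last of these. An emergency admission for infection in an immunosuppressed patient is a natural candidate. This stands, and it limits the point to events whose only seriousness criterion is hospitalisation. It does not close the gap, because the residual criterion rests on judgement whereas admission is an observable trigger.
- **Eligibility narrows the field.** Active infection, serious infection within 8 weeks before Screening, and significant unstable or uncontrolled disease that the investigator thinks could confound results or endanger the patient are excluded (Protocol 5.3.2, criteria 3 and 13). Steroid doses must be stable. Deterioration to admission in such patients may often be called unexpected, which keeps it serious. This also stands in part, but patients with stable comorbidities are eligible and the judgement stays with the site.
- **The sentence is badly built.** It opens with planned care and ends with surgery, so the middle clause could be read as describing elective admissions. That reading is possible. However, *or if* marks a separate alternative, and planned admissions are already exempt by the first clause. The ambiguity is itself a reason to reword.
- **The events are not hidden.** They can be recorded as AEs, every AE is assessed for severity and causality, and the primary endpoint covers AEs as well as SAEs. This stands: what is lost is the serious classification and what follows from it.
- **IDMC oversight.** A reader might infer that the IDMC would not see these events. The documents do not support that. Protocol 8.1.6 has the committee review unblinded safety data, and SAP 4.1 places its outputs in a separate plan that is not available here.

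**Conclusion.** The point holds within limits. As worded, the second exemption allows an unplanned admission for an expected worsening of a comorbidity, where hospitalisation is the only seriousness criterion met, to be classed as a non-serious AE. Such an event gets no 24-hour report, no SUSAR assessment and no place in the serious TEAE count. It can still be recorded as an AE and may appear in the Grade 3 or higher TEAE count.

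This rests on the plain reading of *or if* and on the absence of any narrowing text in either document.

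A reader might infer that every admission for a pre-existing illness ceases to be an SAE, or that sites must record it as non-serious. Neither follows: unexpected deterioration stays serious, the other criteria still apply, and the text permits the non-serious classification through judgement. Nor can a number of lost SAEs be stated, since the documents give no rate of comorbidity admissions. The 8.3 percentage points is the weight of one patient in an arm of 12, in a safety analysis that is descriptive with no tests between groups (SAP 16).

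Worsening of MG is handled by a separate disease-progression rule in 8.1.1, and this point does not depend on it.

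**What to change.** Reword the hospitalisation bullet in Protocol 8.1.1 so that:

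- the exemption covers only admissions or operations planned before informed consent for a condition that has not worsened since;
- an unplanned admission, or a prolongation of a hospital stay, for an AE meets the hospitalisation criterion whether or not the condition pre-existed and whether or not its worsening was expected;
- expectedness plays no part in the seriousness decision. It remains in the SUSAR definition.

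Leave the MG disease-progression rule as it is. Carry the same wording into the SAE form instructions. If only planned admissions were ever meant, the change simply states that intent. No SAP change is needed, because its tables take seriousness as recorded. The cost is one wording change and a few more SAE forms in a trial of about 24 patients.

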16.1. ADVERSE EVENTS

Adverse Events (AEs) will be coded using MedDRA central coding dictionary, Version 19.1.

Treatment-emergent AEs are defined as AEs that first occurred or worsened in severity after the first administration of the IMP. Any AEs started after the informed consent form has been signed and before the first administration of the IMP will be considered as Non-TEAEs.

The relationship to study drug will be summarized as related and unrelated. AEs that are recorded as 'related', 'possibly' or 'probable' in the eCRF are categorized as 'related' whereas the AEs that are recorded as 'unrelated' and 'unlikely' are categorized as 'unrelated'. Missing relationship/missing severity would be considered by the worst case as "Related" and "Grade 5" respectively.

Listings will include TEAEs and Non-TEAEs. Separate listing will be provided for AEs leading to discontinuation, serious adverse events (SAEs) and deaths.

For each treatment group, TEAEs, non-TEAEs, drug related AEs, relationship to study drug, AEs leading to discontinuation and SAEs will be summarized by primary SOC and PT. Also, summary of National Cancer Institute Common Terminology Criteria for Adverse Events (NCI-CTCAE, version 4.03) will be presented by primary SOC and PT. AE tables include number and percentage of subjects and number of events.

An overall summary of adverse events will be produced including frequency counts of:

- number of subjects with at least one TEAE
- number of subjects with at least one non-TEAE
- number of subjects with at least one serious TEAE
- number of subjects withdrawn from treatment with at least one serious TEAE

Document:

CCI

Author:

PPD

Version Number:

1.0

Version Date:

06 Oct 2017

Template No: CCI

Reference: CCI

Effective Date: 01Apr2016

Copyright © 2009, 2010, 2012, 2016 Quintiles Transnational Corp. All rights reserved.

The contents of this document are confidential and proprietary to Quintiles Transnational Corp. Unauthorized use, disclosure or reproduction is strictly prohibited.

- number of subjects with at least one related serious TEAE
- number of subjects who discontinue from the study due to a TEAE
- number of subjects with at least one TEAE with CTCAE severity grade ≥ 3
- number of subjects with at least one related TEAE
- number of deaths

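### The adverse event causality grades do not match the protocol's own reasonable-possibility test: an event with two plausible causes fits no grade fully, and the only grade that accepts another cause is reported as unrelated

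*Protocol*

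**What the plan says.** Protocol 8.1.1 (Adverse Events) contains both the test and the scale.

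- **The test.** "Suspected adverse reaction means any AE for which there is a reasonable possibility that the drug caused the AE". Nothing in that sentence asks for other causes to be excluded.
- **The scale.** Five grades are defined under the Relationship heading. *Possible* applies when "the association of the AE with the IMP is unknown; however, the AE is not reasonably supported by other conditions". *Probable* asks, among other things, that concurrent illness, disease progression "or concomitant medication reactions) do not appear to explain the AE". *Related* asks for a known or expected response pattern, and says of the event that "it cannot reasonably be explained by known characteristics of" the patient's clinical state. An *unlikely* "relationship suggests that only a remote connection exists between the IMP and the reported AE", and its definition continues: "Other conditions, including chronic illness, progression or expression of the disease state, or reaction to concomitant medication, appear to explain the reported AE". *Unrelated* is for events with no reasonable possibility of drug causation.
- **The pooling.** For final reporting, "Unrelated and Unlikely will be clubbed into" one unrelated category, and the other three grades become related. SAP 16.1 uses the same split: "AEs that are recorded as 'unrelated' and 'unlikely' are categorized as 'unrelated".

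SAP 16.1 then counts subjects with a related TEAE and with a related serious TEAE, and tabulates relationship by system organ class and preferred term. Protocol 8.1.1 makes relatedness part of the SUSAR definition, and 8.1.1.1 applies the same relationship criteria to SAEs.

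**The concern.** Safety and tolerability is the primary objective, and the related-event tables are part of how it is reported. ARGX-113 is given on top of background treatment (Protocol 5.2) that may include azathioprine, other immunosuppressants and steroids (5.1), and the drug itself lowers IgG (2.2). Events with two plausible causes are therefore foreseeable. An infection in an immunosuppressed patient is one example.

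For such an event the test and the scale give different answers. The test makes it a suspected adverse reaction. The scale offers no grade that says so, and the one grade that acknowledges the other cause leads to a reported category whose namesake grade is defined by the absence of any reasonable possibility.

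**Working it through.** No sample-size or error-rate arithmetic bears on this point, and the plan states no figure to reproduce. The check is a clause-by-clause comparison. The test case is an event for which the IMP is a reasonable possible cause and another condition also reasonably explains it.

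| Grade | What it asks about the IMP | What it asks about other explanations | Does the test case fit? | Reported as |
|---|---|---|---|---|
| Related | Plausible timing and a known or expected pattern | Not reasonably explained by the patient's clinical state | No, if the rival cause is the clinical state; not clearly excluded if it is only a concomitant drug | Related |
| Probable | Plausible timing, causation likely | Other conditions, including reactions to concomitant medication, do not explain it | No | Related |
| Possible | Association unknown | Not reasonably supported by other conditions | No | Related |
| Unlikely | Only a remote connection | Other conditions appear to explain it | In part: second condition met, first not | Unrelated |
| Unrelated | No reasonable possibility | None stated | No | Unrelated |

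1. **Count of fits.** With another condition as the rival cause, 0 of 5 grades are fully met.
2. **Nearest grade.** *Unlikely* is the only grade that accepts a competing explanation. Choosing it is an inference, because the investigator must pass over the remote-connection clause. Choosing *possible* means passing over its exclusion clause. The text does not settle which clause gives way, so two sites could grade the same event differently.
3. **Narrow exception.** The exclusion in *related* covers the patient's clinical state and, unlike the one in *probable*, does not name concomitant medication. An event with a known pattern whose only rival cause is a background drug could be graded *related* on a literal reading. How often that could apply cannot be judged: this is the first use of ARGX-113 in patients with MG (Protocol 5.2), and the risk assessment in 2.4 is redacted.
4. **Direction.** If the investigator chooses *unlikely*, the event moves to the unrelated row although it satisfies the suspected-reaction test. If the investigator chooses *possible*, the reported category agrees with the test. For these events the error can therefore only lower the related count.
5. **Size.** The number affected would be the number of two-cause events multiplied by the share graded *unlikely*. The documents give neither quantity.

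**The case against.** The strongest reply is that the consequences are contained. Much of it stands.

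- **The safety signal is not hidden.** A reader might infer that a drug-related excess of infections could disappear. It could not: the primary endpoint is the incidence and severity of AEs and SAEs, and SAP 16.1 tabulates TEAEs and SAEs for each arm whatever the causality grade, with a randomised placebo comparison. The IDMC also reviews unblinded safety data after 8 and 16 patients (Protocol 8.1.6).
- **Expedited reporting does not rest on the grade alone.** A reader might infer that SUSARs would be missed. All SAEs are reported within 24 hours whether or not related (8.1.1.1), the sponsor's designee may carry out an independent medical assessment (8.1.1.3), and 8.1.1 lists comparison between groups as evidence of causation. The relatedness judgement is exposed to the flaw, but the documents do not show that it is decided by the site's grade alone.
- **Downward bias is not established.** The definitions say what a grade suggests, not what it requires, so an investigator may still choose *possible*. The documents support inconsistency and a risk of under-counting, not a demonstrated bias.
- **Rival explanations may be fewer than they seem.** Worsening of MG is treated as disease progression, not as an AE (8.1.1). Background drugs must be stable before entry (5.3.1, criterion 5) and held constant (5.1), which weakens them as explanations for new events.

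These points limit the effect but do not repair the wording. None of the safeguards changes the reported category of an event recorded as *unlikely*. The SAP's worst-case rule covers only a missing relationship.

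**Conclusion.** The point holds as a conflict within Protocol 8.1.1 that SAP 16.1 carries forward. An event with a reasonable possibility of drug causation and another plausible explanation fits no grade in full, and can be reported as unrelated. What is exposed is the related-TEAE and related-serious-TEAE tables, the summaries by relationship and the relatedness judgement for SUSARs. The overall AE and SAE tables by arm are not.

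The conclusion rests on the wording alone. Two stronger readings go too far. One is that all three grades pooled as related exclude every rival cause; *related* does not clearly exclude concomitant medication. The other is a count of reclassified patients: multiplying the 12 planned active patients by an assumed share would only restate the assumption, since the documents give no event counts and no grading frequencies.

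**What to change.** In Protocol 8.1.1:

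- Redefine *possible* as a reasonable possibility that the IMP caused the event, although other conditions or concomitant medication could also explain it.
- Limit *unlikely* to a remote connection with a clearly more probable other cause.
- Keep the two-way pooling in 8.1.1 and SAP 16.1 as it is.

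With these definitions the test case meets *possible*, fails *unlikely* because the connection is not remote, and is reported as related, in agreement with the suspected-reaction test.

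If events have already been graded under the present wording, do not regrade them. Add a TEAE table by the five recorded grades to SAP 16.1, so that readers can see how many *unlikely* events sit in the unrelated category. The eCRF already records the five grades, so this needs no new data. The documents do not say whether grading has begun, but the protocol is dated November 2016 and the SAP October 2017, so this may be the route that applies.

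**Cost.** Two sentences in 8.1.1 and matching eCRF instructions, or one extra table. More events may be reported as related, which makes that table slightly less favourable. Changing the definitions after enrolment has begun needs an amendment with ethics approval (5.3.7), briefing of sites, and a note in the study report that two definitions were used within a trial of about 24 patients.
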